#### **6.4 Study Completion**

Subjects will be followed for 6 months after stent removal.

Additional visits may be conducted at the Investigator's discretion in accordance with Adverse Event or Device Event data collection. A subject will be considered lost to follow-up if the subject remains unresponsive to communication after three documented attempts by study staff.

## **6.5 Source Documents**

The Investigator/institution guarantees direct access to original source documents, including imaging documentation, by BSC personnel, their designees, and appropriate regulatory authorities. In the event that the original medical records cannot be obtained for a patient that is seen by a non-study physician at a non-study institution, photocopies of the original source documents must be made available for review.

## **7 Statistical Considerations**

### **7.1 Effectiveness Endpoint**

#### Primary Effectiveness Endpoint:

The primary effectiveness endpoint for this study is the resolution of WON with endoscopic drainage defined as radiographic decrease of WON size to  $\leq 3$ cm evaluated by CT scan or MRI

#### Primary Effectiveness Endpoint Assessment:

*Note: Success will be based on the number of WONs resolved, not on the number of AXIOS™ Stents required to achieve resolution.*

- If it is determined that the fluid collection is actually two separate collections, and each collection is drained via an AXIOS™ stent, then each collection will be assessed individually via the drainage success criteria of  $\leq 3$ cm.
- If it is determined that the fluid collection is a single collection but the drainage is inadequate via a single AXIOS™ stent, then the success of the AXIOS™ drainage will be assessed as follows:
  - If a second AXIOS™ stent is used at a new drainage site/original drainage site and the entire fluid collection is drained to meet the success criteria of  $\leq 3$ cm then the collection will be considered to be a single collection drainage success.
  - If a second AXIOS™ stent is used at a new drainage site and the entire fluid collection does not drain adequately to meet the drainage success criteria of  $\leq 3$ cm then the fluid drainage of the collection will be considered to be a single drainage failure.
  - If a plastic stent is used at a new drainage site and the entire fluid collection drains to meet the drainage success criteria of  $\leq 3$ cm then the fluid drainage will be considered indeterminate.

- If a single, 7fr plastic stent is used at the same drainage site, through the AXIOS™ stent, and the entire fluid collection drains to meet the drainage success criteria of  $\leq 3$ cm then the fluid drainage will be considered a single collection drainage success.
- If a plastic stent is used at a new drainage site and the entire fluid collection does not drain to meet the drainage success criteria of  $\leq 3$ cm then the fluid drainage will be considered a single drainage failure.

Hypothesis:

As in the original IDE, #G130264, there is no formal statistical hypothesis for this study. The proportion of AXIOS patients with reduction of WON size to  $\leq 3$ cm within 60 days from AXIOS™ stent placement in the original IDE is 76.7% (23/30) [95% CI (57.7%, 90.0%)] patients. Given that the WONs in the proposed IDE will have an estimated necrotic material content above 30%, namely larger than in IDE #G130264, a slightly lower success rate of 70% is expected in this study. This success rate is within the range of reported WON resolution rates in several recent publications [2-8] representing 448 patients for which a random effects meta-analysis yields a mid-point WON resolution rate of 67.0% [95% CI (60.0%, 73.4%)] for WON drainage with plastic stents (Table 7.1), an established WON drainage method as described in the ASGE guidelines on treatment of pancreatic fluid collections [9].

**Table 7.1 Plastic Stent WON Resolution Rates from Recent Publications**

Study	% Resolution (x/N)	95% Confidence Interval
Bapaye (2017)	73.8% (45/61)	(60.9%, 84.2%)
Gardner et al (2009)	68.9% (31/45)	(53.4%, 81.8%)
Papachristou (2007)	52.8% (28/53)	(38.6%, 66.7%)
Schmidt (2015)	61.7% (50/81)	(50.3%, 72.3%)
Smoczynski (2015)	75.9% (85/112)	(66.9%, 83.5%)
Abu [name] (2017)	75.0% (27/36)	(57.8%, 87.9%)
Varadarajulu (2011)	60.0% (36/60)	(46.5%, 72.4%)
Random-Effects Meta-Analysis	67.0%	(60.0%, 73.4%)

Statistical Methods:

The primary effectiveness endpoint will be summarized as the proportion of patients who have resolution of WON with endoscopic drainage defined as radiographic decrease of WON size to  $\leq 3$ cm evaluated by CT scan or MRI out of all patients who have an AXIOS™ stent successfully implanted. A Clopper-Pearson exact 95% confidence interval will also be calculated.

**7.2 Safety Endpoint**

Primary Safety Endpoint:

The Primary Safety Endpoint is AXIOS™ stent related or WON drainage procedure related serious adverse events.

Primary Safety Endpoint Assessment:

If it is determined that the patient has an infection, then the primary safety success of the AXIOS™ device or the drainage procedure will be assessed as follows:

- If the patient presents with an infected collection at the initial drainage procedure, the infection will be classified as a localized infection and will not be considered a stent related or WON drainage related serious adverse event
- If the patient presents with a sterile collection at the initial drainage procedure and post-procedurally develops an infected collection, the infection will be classified as a localized infection and will not be considered a stent related or WON drainage related serious adverse event as this is a known consequence of any endoscopic drainage procedure, where the access route to the collection is through a non-sterile GI lumen and is not a function of a particular stent or device

*(Note: If the stent is occluded at the onset of infection, then the infection will be attributed to the device. If the stent remains unobstructed at the time of infection, then the infection will not be attributed to the device.)*

- If the patient presents with a sterile collection at the initial drainage procedure and then post-procedurally develops a wide-spread infection in the form of sepsis or blood stream infection, then the infection will be classified as systemic and will be considered a stent related or WON drainage related serious adverse event only if the AXIOS stent was clearly and visually occluded by solid necrosis at the time of repeat endoscopy. This determination will be made by the operating physician at the time of endoscopy

Hypothesis:

As in the original IDE, #G130264, there is no formal statistical hypothesis for this study. The proportion of AXIOS patients with AXIOS™ stent related or WON drainage procedure related serious adverse events in the original IDE is 10.0% (3/30) [95% CI (2.1%, 26.5%)] patients. A similar rate of AXIOS™ stent related or WON drainage procedure related serious adverse events is expected in this study. This event rate is within the range of reported stent related or WON drainage procedure related serious adverse event rates in several recent publications [3-5, 10] representing 306 patients for which a random effects meta-analysis yields a mid-point related SAE rate of 16.7% [95% CI (10.1%, 26.3%)] for WON drainage with plastic stents (see Table 7.2 and Table 7.3 (categorized events from Table 7.2)), an established WON drainage method as described in the ASGE guidelines on treatment of pancreatic fluid collections [9].

**Table 7.2 Plastic Stent-related or WON Drainage-procedure related Serious Adverse Events Rates from Recent Publications [3-5, 10]**

Study	% Related SAEs (x/N)	95% Confidence Interval
Papachristou (2007)	20.8% (11/53)	(10.8%, 34.1%)
Schmidt (2015)	12.3% (10/81)	(6.1%, 21.5%)
Smoczynski (2015)	25.9% (29/112)	(18.1%, 35.0%)
Varadarajulu (2011)	8.3% (5/60)	(2.8%, 18.4%)
Random-Effect Meta-Analysis	16.7%	(10.1%, 26.3%)

**Table 7.3 Categorized Plastic Stent-related or WON Drainage-procedure related Serious Adverse Events Rates from Recent Publications [3-5, 10]**

SAE	% (x/N)
Bleeding	11.1% (34/306)
Perforation	2.6% (8/306) [5 GI; 2 Collections; 1 Undefined]
Pneumoperitoneum	1.3% (4/306)
Sepsis	0.7% (2/306)*
Stent migration	1.0% (3/306)
Multiple organ failure	1.0% (3/306)
Other - loss of access to the collection (due to hypertension)	0.3% (1/306)

\*Note: 1 patient with septic shock also had multiple organ failure (death)

#### Statistical Methods:

The primary safety endpoint will be summarized as the proportion of patients who have AXIOS™ stent related or WON drainage procedure related serious adverse events out of all patients who have an AXIOS stent successfully implanted. A Clopper-Pearson exact 95% confidence interval will also be calculated.

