### **5.4 Withdrawal**

All subjects enrolled in the clinical study (including those withdrawn from the clinical study or lost to follow-up) shall be accounted for and documented. If a subject withdraws from the clinical investigation, the reason(s) shall be reported. If such withdrawal is due to problems related to investigational device safety or performance, the investigator shall ask for the subject’s permission to follow his/her status/condition outside of the clinical study.

Reasons for withdrawal include physician discretion, subject choice to withdraw consent, loss to follow-up and death. While study withdrawal is discouraged, subjects may withdraw from the study at any time, with or without reason, and without prejudice to further treatment. All applicable case report forms up to the point of subject withdrawal must be completed. Additional data may no longer be collected after the point at which a subject has been withdrawn from the study or withdraws his/her consent, for whatever reason. All open

adverse events should be closed or include resolution status. Data collected up to the point of subject withdrawal may be used. Withdrawn subjects will not be replaced. Subjects who withdraw from the study with the study stent in place will be followed per standard of care at the local institution.

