#### Treated Cohort

The treated cohort is defined as all ITT subjects who have an AXIOS™ stent implanted for the purpose of WON drainage. Subjects in the treated cohort will be counted towards the enrollment ceiling and this cohort will be considered the primary analysis cohort.

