### **7.3 Sample Size and Success Criteria**

The WON resolution rates and related SAE rates reported in the above provided study references are similar to those reported for WON drainage using plastic stents in a recent systematic review and meta-analysis comparing plastic stents to metal stents, including lumen-apposing metal stents (LAMS) for the management of WONs [28]. Appendix I in Section 21 provides a few key points from this systematic review.

Although reported effectiveness and safety event rates from different sources appear similar, 95% confidence intervals are fairly wide, mostly due to small sample sizes and heterogeneity in WONs and in detailed procedural WON drainage steps. Therefore we chose to increase the sample size of the present study to be slightly larger than in the original IDE study #G130264, which was 30 patients.

We will conduct the present study in 40 patients.

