#### Safety Endpoint Success Criteria

An observed rate of 17.5% or lower for the proportion of AXIOS patients with AXIOS™ stent related or WON drainage procedure related serious adverse events is required for success.

This rate is similar to the point estimate of the random-effect meta-analysis of AXIOS stent related or WON drainage related serious adverse events provided in Table 7.2. Note that in the recent systematic review and meta-analysis [28] (Appendix I in Section 21) the complication rates that showed statistically significant differences between plastic stents and LAMS for drainage of WONs were bleeding and stent occlusion, both in favor of LAMS. These findings are particularly important given that (a) bleeding is the most commonly reported serious adverse event, and (b) stent occlusion almost always requires reintervention. It should also be noted that of the plastic stent WON drainage references provided above, even the one reporting the highest complication rates, namely Smoczynski et al [5] conclude that the benefits outweigh the risks: *“In a large group of selected patients with symptomatic walled-off necrosis, endoscopic drainage enables high success rate with acceptable complication rate and low procedure-related mortality.”* Thus the proposed success criteria for safety seems reasonable and acceptable.

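### A patient lost without a recorded related SAE counts as event-free in the primary safety proportion, and the pass mark sits exactly at 7/40 with no check for losses

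*Protocol*

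**What the plan says.** Protocol 7.2 (Statistical Methods) and SAP 3.2.2 give the same formula: patients with a stent-related or drainage-procedure-related SAE "out of all patients who have an AXIOS stent successfully implanted", with a Clopper-Pearson 95% interval. This is the treated cohort, and under Protocol 5.5 "this cohort will be considered the primary analysis cohort".

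The success rule (Protocol 7.3, SAP 3.3.2) is "An observed rate of 17.5% or lower for the proportion of AXIOS patients" with a related SAE. It applies to the point estimate only; no confidence limit is tied to it. On size, Protocol 7.3 says "We will conduct the present study in 40 patients".

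On losses, Protocol 5.4 says "Withdrawn subjects will not be replaced" and "Additional data may no longer be collected after the point at which a subject has been withdrawn from the study". It also allows data gathered before withdrawal to be used. SAEs are reportable until the study ends (Protocol Table 15.4-1), and follow-up runs to 6 months after stent removal (Protocol 6.4). The safety endpoint has no time window of its own, whereas the effectiveness criterion is tied to 60 days.

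SAP 5.6.3 tabulates the number lost by visit. Neither document has a missing-data rule for safety, a minimum follow-up, a censored estimate or a sensitivity analysis for losses. The per-protocol analysis does not fill the gap, because that cohort is defined by eligibility and not by follow-up (Protocol 5.5, SAP 4.2).

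**The concern.** A patient who leaves with no related SAE on record adds 1 to the denominator and 0 to the numerator, however short the follow-up. Compared with complete capture, this either leaves the observed rate unchanged or lowers it, so any error favours the device. The same denominator works the other way for effectiveness, where a patient without a qualifying scan is not counted as resolved. The plan does not remark on this difference.

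At stake is the safety verdict. It is a yes/no reading of a point estimate from 40 patients, and the limit coincides with an attainable value. A single unseen event at that boundary changes the conclusion, and nothing in the planned output would show whether the verdict depends on the patients who were lost.

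**Working it through.** **Inputs.** 40 implanted patients and a 17.5% limit (Protocol 7.3). Expected rate 10.0%, from 3/30 in the sponsor's preceding IDE study, and a literature benchmark of 16.7% (both Protocol 7.2). The dropout rate and the timing of SAEs are not given, so the share of events unseen is an assumption, shown over a range.

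**The plan's own figures reproduce.** The Clopper-Pearson interval for 3/30 is 2.1% to 26.5%, as stated. DerSimonian-Laird random effects on the logit scale for 11/53, 10/81, 29/112 and 5/60 give 16.67% (10.06%, 26.34%), matching the stated 16.7% (10.1%, 26.3%). The sample size of 40 has no formula to check, since no hypothesis is stated.

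**Where the cut falls.** 0.175 × 40 = 7. So 7/40 = 17.5% passes and 8/40 = 20.0% fails. If 8 patients truly have a related SAE and one of these is lost before it is recorded, the written rule returns 7/40 and passes.

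**Chance of passing.** Let p be the true rate and h the share of related SAEs unseen because of loss, each event being missed independently. The observed count X is Binomial(40, p(1 − h)), and P(pass) = P(X ≤ 7).

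| True rate p | h = 0 | h = 5% | h = 10% | h = 20% |
|---|---|---|---|---|
| 10% (expected) | 0.958 | 0.968 | 0.976 | 0.987 |
| 16.7% (benchmark) | 0.651 | 0.704 | 0.754 | 0.843 |
| 20% | 0.437 | 0.501 | 0.566 | 0.696 |
| 25% | 0.182 | 0.233 | 0.294 | 0.437 |

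The gain over h = 0 is the probability that 8 or more events occur but 7 or fewer are seen. At p = 20% it is 0.064, 0.129 and 0.258 for h = 5%, 10% and 20%. True rates of 20% and 25% lie inside both intervals quoted in Protocol 7.2.

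**What two standard checks would show.** Let k be the number of patients with a recorded event and L the number lost without one.

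- Followed patients only, k/(40 − L): 7 events exceed the limit with 1 loss (7/39 = 17.9%); 6 events need 6 losses (6/34 = 17.6%); 5 events need 12 (5/28 = 17.9%).
- Worst case, (k + L)/40: the limit is exceeded once k + L reaches 8, that is 7 + 1, 6 + 2, 5 + 3 or 4 + 4, each 8/40 = 20.0%. At the expected 10% (4 events), four losses would leave the verdict open under this bound.

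**The case against.** Counting all implanted patients is the usual safety denominator and should stay primary. The study is descriptive, an exact interval is reported (7.3% to 32.8% for 7/40), and losses are tabulated, so a reader is not wholly uninformed. At the rate the plan expects, the effect is small. All of this stands. It limits the size of the point but does not supply the missing check.

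Three stronger readings are tempting, and the documents do not support them.

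- A reader might infer that everyone lost is counted as SAE-free. Protocol 5.4 allows data up to withdrawal to be used, so a related SAE recorded before loss counts. A related death also counts, because Protocol 15.1 records death as the outcome of an SAE.
- A reader might take 7/39 = 17.9% as the true rate that 7/40 conceals. It is only a different denominator, with no missed event shown. It is itself biased upward, because it discards the event-free time of patients followed for part of the period while keeping early events.
- A reader might assume that nothing is learned after loss. Protocol 5.4 has the investigator ask permission to follow patients who withdraw because of device safety or performance. Section 5.6 adds contact attempts while a stent is in place, and section 6.5 provides for records from non-study institutions. These steps lessen the problem but set no analysis rule.

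Nor is 10% of patients lost the same as 10% of events unseen. If loss is unrelated to SAE risk and some events come before loss, the unseen share is smaller than the dropout rate, and more so if related SAEs cluster around the procedure.

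**Conclusion.** The point holds in a limited form. The written formula treats a patient lost without a recorded related SAE as event-free. The direction of the resulting error is known and favourable, and neither document plans an analysis that would reveal it. This status follows from the formula and the absence of a missing-data rule; it is not stated as a rule.

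The size depends on how close the result is to the limit. One unseen event is decisive at 8/40. With 10% of events unseen, the chance of passing gains 0.129 at a true 20%, 0.103 at 16.7% and 0.018 at 10%. These figures assume 40 implanted patients and independent missing of events. The documents do not show that losses will be common or that a failing result will in fact be turned into a pass. The unstated safety window is part of the same gap, because without it complete follow-up cannot be defined. This is a low-cost improvement worth making, and it does not invalidate the primary analysis.

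**What to change.** Keep the all-implanted proportion as the primary safety result. State in Protocol 7.2 and SAP 3.2.2 the time window it covers, so that losses at any point within that window are addressed. Then prespecify in SAP 3.2.2, each reported against 17.5%:

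1. The rate among patients followed through the window or with an earlier related SAE, with a note that it is biased upward because it drops partial event-free follow-up. Alternatively, a Kaplan-Meier estimate that censors losses and so uses that partial time, on the assumption that loss is unrelated to SAE risk.
2. A worst-case or tipping-point count: how many of the patients lost without a recorded related SAE would need to have had one for the rate to exceed 17.5%.

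The worst case is an extreme bound and should be labelled as such. The tipping-point form is easier to read, because it lets the reader judge whether the required number is plausible. The cost is one extra table, and a safety result that may look slightly less favourable. If losses are few, the same table supports the primary result.

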### **7.3 Sample Size and Success Criteria**

The WON resolution rates and related SAE rates reported in the above provided study references are similar to those reported for WON drainage using plastic stents in a recent systematic review and meta-analysis comparing plastic stents to metal stents, including lumen-apposing metal stents (LAMS) for the management of WONs [28]. Appendix I in Section 21 provides a few key points from this systematic review.

Although reported effectiveness and safety event rates from different sources appear similar, 95% confidence intervals are fairly wide, mostly due to small sample sizes and heterogeneity in WONs and in detailed procedural WON drainage steps. Therefore we chose to increase the sample size of the present study to be slightly larger than in the original IDE study #G130264, which was 30 patients.

We will conduct the present study in 40 patients.

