#### Effectiveness Endpoint Success Criteria

An observed rate of 67% or higher for the proportion of AXIOS patients with reduction of WON size to  $\leq 3$ cm within 60 days from AXIOS™ stent placement is required for success.

This rate is the same as the point estimate of the random-effect meta-analysis of WON resolution rates provided in Table 7.1. Note that in the recent systematic review and meta-analysis [28] (Appendix I in Section 21) WON resolution rates were higher and number of procedures required to reach WON resolution were lower when using LAMS compared to plastic stents for WON drainage. Thus the proposed success criteria for effectiveness seems reasonable.

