3.3.1 Effectiveness Endpoint Success Criteria

An observed rate of 67% or higher for the proportion of AXIOS patients with reduction of WON size to ≤ 3 cm within 60 days from AXIOS™ stent placement is required for success.

This rate is the same as the point estimate of the random-effect meta-analysis of WON resolution rates for plastic stents provided in Table 1. Note that in the recent systematic review and meta-

analysis [10] (Appendix I in Section 21 of the protocol) WON resolution rates were higher and the number of procedures required to reach WON resolution were lower when using LAMS compared to plastic stents for WON drainage. Thus, the proposed success criteria for effectiveness seems reasonable.

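### Does the cited review's 80.9% plastic-stent resolution rate undercut the 67% effectiveness criterion?

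*Protocol*

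**What the plan says.** Protocol 7.1 (Hypothesis) and SAP 3.1.1 draw on "reported WON resolution rates in several recent publications [2-8] representing 448 patients" and pool seven plastic-stent studies to 67.0% (60.0% to 73.4%). The same paragraph gives the planning value for this trial: "a slightly lower success rate of 70% is expected in this study".

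Protocol 7.3 and SAP 3.3 then compare these studies with a published systematic review of metal versus plastic stents, saying that their rates "are similar to those reported for WON drainage using plastic stents in a recent systematic review and meta-analysis". The next paragraph repeats the idea: "Although reported effectiveness and safety event rates from different sources appear similar". Extracts from the review are in Protocol Section 21, Table A1.

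The effectiveness criterion is an observed rate of 67% or higher for reduction to 3 cm or less within 60 days. Its source is stated: "This rate is the same as the point estimate of the random-effect meta-analysis of WON resolution rates provided in Table 7.1". The review comes in afterwards, for the finding that "WON resolution rates were higher and number of procedures required to reach WON resolution were lower when using LAMS compared to plastic stents", and the paragraph ends "Thus the proposed success criteria for effectiveness seems reasonable". SAP 3.3.1 says the same.

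**The concern.** A reader who follows the reference to Section 21 finds plastic-stent overall resolution of 80.9%. That is above the upper confidence limit of Table 7.1 and above every one of its seven studies. The plan does not discuss the gap. Neither Table 7.1 nor Table A1 gives a size cut-off or time window for resolution, so the documents alone cannot show whether the two figures measure the same thing.

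The trial has no control arm and no hypothesis test, so the observed rate of 67% is its only effectiveness rule. If the true plastic-stent rate on the trial's own definition were nearer 81%, a result just above 67% would look like parity with plastic stents when it was not. In counts, 67% of 40 means at least 27 successes (0.67 × 40 = 26.8), and 80.9% would mean at least 33 (0.809 × 40 = 32.4). It also looks awkward that the review is used to call the criterion reasonable while its printed overall rates, 80.9% for plastic and 91.5% for LAMS, both lie above it.

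**Working it through.** **1. Reproduce the plan's figure.** Inputs are the seven counts in Table 7.1: 45/61, 31/45, 28/53, 50/81, 85/112, 27/36 and 36/60. The method is DerSimonian-Laird on the logit scale, with y = ln[x/(N−x)], v = 1/x + 1/(N−x) and w = 1/v.

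| x/N | y | v | w | w* = 1/(v+τ²) |
|---|---|---|---|---|
| 45/61 | 1.034 | 0.0847 | 11.80 | 5.692 |
| 31/45 | 0.795 | 0.1037 | 9.64 | 5.137 |
| 28/53 | 0.113 | 0.0757 | 13.21 | 5.999 |
| 50/81 | 0.478 | 0.0523 | 19.14 | 6.982 |
| 85/112 | 1.147 | 0.0488 | 20.49 | 7.155 |
| 27/36 | 1.099 | 0.1481 | 6.75 | 4.182 |
| 36/60 | 0.405 | 0.0694 | 14.40 | 6.234 |

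- Fixed-effect mean = Σwy/Σw = 0.705, and Q = Σw(y − 0.705)² = 13.30 on 6 df.
- Σw = 95.43 and Σw² = 1445.8, so τ² = (13.30 − 6)/(95.43 − 1445.8/95.43) = 7.30/80.28 = 0.091. I² = 7.30/13.30 = 55%.
- Random-effects mean = Σw*y/Σw* = 29.314/41.381 = 0.708, with SE = 1/√41.381 = 0.155.
- Back-transformed, this is 67.0%, with limits from 0.708 ± 1.96 × 0.155 of 60.0% and 73.4%.

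The plan's estimate and interval are reproduced exactly, so the 67% is arithmetically sound.

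**2. Compare with the review's extract.** Table A1 shows two plastic-stent resolution rates, both from two-arm studies and both without a confidence interval.

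- Overall: 80.9 − 67.0 = 13.9 points above the pooled rate, and 80.9 − 73.4 = 7.5 points above the upper limit. The highest single study in Table 7.1 is 75.9%.
- Single procedure: 67.0 − 43.4 = 23.6 points below the pooled rate, and below the lower limit of 60.0%.

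Neither rate lies in the plan's interval, so the similarity statement is not supported for resolution. Which of the two is nearer to 67.0% in meaning depends on how resolution is defined.

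**3. Is the gap surprising?** Four of the seven study intervals in Table 7.1 include 80.9% (upper limits 84.2%, 81.8%, 83.5% and 87.9%). Three exclude it (66.7%, 72.3% and 72.4%). The 95% prediction interval for a new study's true rate is 0.708 ± 2.571 × √(0.091 + 0.155²) on the logit scale, which is 45.9% to 82.9% and covers 80.9%. That is only a rough guide, because 80.9% is itself a summary over studies.

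The same device in the sponsor's earlier study gave 76.7% (23/30) on the 3 cm, 60-day measure, against 91.5% for LAMS in the review. The difference, 14.8 points, has the same direction and about the same size. A stricter definition in the trial would produce this pattern, but with 30 patients it is suggestive only.

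**4. What the criterion takes from the review.** Only direction. Table A1 gives LAMS 91.5% against plastic 80.9%, printed odds ratio 2.5 (1.4 to 4.3). As a check, (0.915/0.085)/(0.809/0.191) = 10.76/4.24 = 2.5. The statement quoted from the effectiveness criterion is therefore supported, and it does not need the two plastic-stent levels to agree.

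**5. What the sentence controls.** The criterion comes from Table 7.1. The sample size of 40 is explained by wide intervals and by an earlier study of 30 patients. The analysis is a proportion with a Clopper-Pearson interval. None of these uses the similarity statement. At the planning rate of 70%, P(X ≥ 27 | n = 40) = 0.703 however the sentence reads.

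**The case for a change.** The strongest case for acting is that a single-arm trial stands or falls on its benchmark. The plan shows a higher plastic-stent figure and passes over it with one adjective. The only account of variation it gives, differing collections and drainage technique, is offered for the width of the intervals and not for this gap. Seven studies with 448 patients are described just as recent publications, while the review covers 1202 plastic-stent patients. Adding each study's definition, time window and necrotic fraction would let a reader judge whether 67% is on the trial's scale.

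Much of this stands. The adjective is wrong for resolution on the figures shown, and the definitions would be useful background.

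It does not carry through to a change. Section 21 is presented as a few key points, with no one-arm resolution rate and no interval for the plastic-stent resolution rates, so it cannot show that 67% is mistaken. The concern itself does not argue for 80.9%. Any re-derivation would depend on definitions not in the plan, and its outcome would be debatable. It would also reopen criteria that the Protocol revision history (Rev F) records as modified, together with the addition of the meta-analysis, after regulator feedback.

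**Conclusion.** The wording is imprecise, and correcting it would have no effect on the trial. The similarity statement fails for resolution: 67.0% against 80.9% overall, a gap of 13.9 points, and 43.4% with a single procedure. The criterion of 67%, or 27 of 40, rests on a correctly computed estimate from named studies, and the review is used only for a direction that its figures support. Changing the sentence would alter no criterion, sample size, analysis or conclusion.

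Both sets of figures are printed in the protocol, so whoever interprets the result can set them side by side and note that definitions of resolution may differ between sources.

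This conclusion assumes that the Table 7.1 studies measure resolution closely enough to the trial's 3 cm, 60-day definition to serve as an agreed reference. The documents neither confirm nor refute that. If it proved false, the question would be the choice of benchmark and not this sentence.
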